2.0 OBJECTIVES AND SCIENTIFIC AIMS

- To assess the feasibility of combining intrathecal radioimmunotherapy with external beam radiation therapy and chemotherapy.
- To maintain or exceed the current progression-free survival rate for patients with standard-risk medulloblastoma while using the protocol-prescribed regimen that is hypothesized to have less long-term serious morbidity.
- To evaluate the long-term morbidities in patients treated with this regimen, with specific attention to neuropsychological, neuroendocrine, audiometric and growth outcomes.

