8.0 PRETREATMENT EVALUATION

- Review of the pathology by the Memorial Sloan-Kettering Cancer Center Department of Pathology

- Post-operative head MRI
- Spine MRI
- CSF cytology obtained via lumbar puncture
- 111-Indium DTPA CSF flow study
- Liver function tests: Total bilirubin, AST
- Renal function tests: Creatinine clearance or nuclear GFR study
- For females \geq 12-years-old, pregnancy test
- All of these pre-treatment evaluations (other than pathology review) should have been performed \leq 30 days before registration onto study

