10.0 EVALUATION DURING TREATMENT/INTERVENTION

A tabular summary of the timing of the mandated observations is included as an appendix to the protocol.

Dosimetry studies during phase 1 of the protocol (see section 9.1).

CBC will be obtained about weekly during external beam radiation therapy.

CBC, total bilirubin, AST, creatinine clearance or GFR, and audiograms will be obtained at baseline and prior to each cycle of cisplatin-containing chemotherapy.

Serum for anti-idiotypic testing (order as Research test: 1 red top tube to be sent to [name] laboratory, Z-1431) will be obtained about every 6 months.

Neuropsychological battery will be performed at "baseline", and at about 1 year and 4 years post-completion of treatment. The "baseline" testing may be performed up to 4 months post-completion of external beam radiation therapy.

The tests in the assessment battery are presented in Table 1 below for parents and children by age and by functional domain assessed. The attending neuropsychologist may

**Memorial Sloan-Kettering Cancer Center
IRB Protocol**

IRB#: 02-088A(5)

make necessary modifications to the battery as indicated for an individual patient's special circumstances without it being considered a protocol violation.

**IRB
PB**

Amended: 2/26/08

Table 1. Neuropsychological and Behavioral Battery

Test	Child's Age				
	> 3 & ≤ 4 yrs	>4 & ≤ 6 yrs	> 6 & ≤ 12 yrs	> 12 & ≤ 16 yrs	> 16 yrs
Children					
Intelligence					
WPPSI-III (Vocabulary, Block Design) (15 min)	X	X			
WISC-IV (Vocabulary, Block Design) (15 min)			X	X	
WAIS-III (Vocabulary, Block Design) (15 min)					X
Processing Speed/Attention					
WPPSI-III (Symbol Search, Coding) (10 min)	X	X			
WISC-IV (Symbol Search, Coding) (10 min)			X	X	
WAIS-III (Symbol Search, Coding) (10 min)					X
Memory					
NEPSY (Story Memory) (5 min)	X (3-5 yrs)				
CMS (15 min)		X (≥ 5 yrs)			
CVLT-C (15 min)		X (≥ 5 yrs)			
WISC-IV (Digit Span) (5 min)			X	X	
WAIS-III (Digit Span) (5 min)					X
WMS-III and CVLT-II (20 min)					X
Parents					
Attention and Behavior/Social/Emotional Function					
BASC-II (20 min)	X				
Executive Function					
BRIEF (5 min)	X	X	X	X	X
Quality of Life					
PedsQL 4.0 (Generic Version)	X	X	X	X	X

Index of Test Abbreviations

WPPSI-III	Wechsler Preschool and Primary Scale of Intelligence – 3 rd Edition
WISC-IV	Wechsler Intelligence Scales for Children – 4 th Edition
WAIS-III	Wechsler Adult Intelligence Scales – 3 rd Edition
NEPSY	NEPSY: A Developmental Neuropsychological Assessment

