14.0 BIOSTATISTICS

A total of 20 patients will be enrolled on this pilot study. We have recently seen 3 to 4 patients per year potentially eligible for this study at MSKCC, but it is anticipated that the unique approach proposed in this protocol will allow accrual to be approximately 6 patients per year.

Children with standard-risk medulloblastoma have been reported to achieve 3-year progression-free survival of 86%. Of those who failed, half failed within the first 2 years of diagnosis.² CCG-9961 expanded the approach to a larger group of patients, but outcome data are not yet available. If they become available during the conduct of this trial, the statistical considerations described in this section will be revised if necessary.

We will stop the trial if 6 or more patients fail before 3 years. The likelihood of stopping the trial is only 7% if the true 3-yr PFS is comparable to the control data (85%), and increases to 23% if the true PFS is 75% and to 76% if the true 3-yr PFS is only 65%.

Neuropsychological test results will be reported in tabular format for each evaluation time (baseline, and annual post-treatment), using means and standard deviations or medians and ranges, as appropriate. They will be reported both as raw scores and as age/sex-adjusted "z-scores" and tracked for changes over time relative to baseline. Thus, given the relatively small sample size of 20 patients, the analysis of these scores for evidence of neurotoxicity, or lack thereof, will primarily be descriptive.

Should the results of this trial be encouraging, future possibilities would include use of this strategy on a larger scale through the Children's Oncology Group, and/or additional institutional study of further decrease of the craniospinal RT dose, possibly in conjunction with the use of an increased radioimmunotherapy dose.

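### The neuropsychological baseline may be taken up to 4 months after radiotherapy, and Section 14 measures change from it without regard to when it was taken

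*Combined protocol and SAP*

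**What the plan says.** Section 2.0 makes neuropsychological outcome part of the third objective: "To evaluate the long-term morbidities in patients treated with this regimen, with specific attention to neuropsychological" and other outcomes.

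Section 10.0 schedules the battery at baseline "and at about 1 year and 4 years post-completion of treatment". It puts the word baseline in quotation marks and adds that this test "testing may be performed up to 4 months post-completion of external beam radiation therapy". It sets no earliest date and does not require a test before treatment.

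Section 8.0 lists what is done before registration: "All of these pre-treatment evaluations (other than pathology review) should have been performed" within 30 days. No neuropsychological test is on that list.

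Section 14.0 tabulates results "for each evaluation time (baseline, and annual post-treatment". On the scores it says: "They will be reported both as raw scores and as age/sex-adjusted" z-scores, "tracked for changes over time relative to baseline". With 20 patients, "the analysis of these scores for evidence of neurotoxicity, or lack thereof, will primarily be descriptive". Nothing there refers to when the baseline was taken.

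Table 1 in Section 10.0 assigns instruments by age: WPPSI-III up to 6 years, WISC-IV over 6 up to 16, WAIS-III over 16. The instrument descriptions after the table instead give WPPSI-III for under 7 and WISC-IV for 7 to 16.

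**The concern.** A change score can show only what happened after its starting point. If a patient's baseline is taken after the injections and radiotherapy, any effect already present at that test is built into the reference and cancels out. A small change in such a patient could then be read as a lack of neurotoxicity, when it says nothing about the period before the test.

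If baseline timing varies between patients, one mean and standard deviation combine two quantities: change across the whole regimen and change after radiotherapy. If all patients are tested late, the summary is consistent but still starts after radiotherapy.

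A second problem affects the same table. Raw scores from different Wechsler instruments are not on one scale, so subtracting one from the other has no clear meaning. Section 14 plans raw scores as well as z-scores and does not say what happens when a child moves to another instrument.

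There is no formal test here, but the summaries will be used. Section 14 says encouraging results could lead to larger-scale use or a further cut in craniospinal dose.

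**Working it through.** The plan states no figure on this point, so there is none to reproduce. The check places the latest permitted baseline on the planned schedule.

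Inputs:
- Section 9.1.2: two injections about 1 week apart.
- Section 9.2: 5400 cGy in total at 180 cGy per day, 5 days per week. Radiotherapy follows recovery from the injections; the gap is not stated and is set to 0.
- Section 9.3: 8 weekly vincristine doses from about the start of radiotherapy. Then 8 cycles, starting about 6 weeks after radiotherapy and repeating about every 6 weeks, with 3 vincristine doses each.
- Section 10: baseline up to 4 months after radiotherapy; follow-up tests about 1 and 4 years after treatment.
- Conversion: 4 months = 4 × 365.25 / 12 / 7 = 17.4 weeks; 1 year = 52.2 weeks.
- Assumption: treatment is complete between week 50 (48 + 2, last vincristine of cycle 8) and week 54 (48 + 6, end of cycle 8) after radiotherapy.

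What has been given by the latest baseline:
- Radiotherapy: 5400 / 180 = 30 fractions; 30 / 5 = 6 weeks. All 30 are complete.
- Cycles start 6, 12, 18, …, 48 weeks after radiotherapy. By week 17.4, 2 of 8 have started.
- Vincristine: 8 + 2 × 3 = 14 of 8 + 8 × 3 = 32 planned doses.
- Time from radiotherapy start: 6 + 17.4 = 23.4 weeks. From first injection: 1 + 6 + 17.4 = 24.4 weeks, a lower bound because the gap was set to 0.

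What the change scores span:
- 1-year test: 50 + 52.2 = 102.2 to 54 + 52.2 = 106.2 weeks after radiotherapy. From the latest baseline, 84.8 to 88.8 weeks, or 1.62 to 1.70 years. From the first injection, at least 109.2 to 113.2 weeks, or 2.09 to 2.17 years. Share before the latest baseline: 24.4 / 109.2 to 24.4 / 113.2, about 22%.
- 4-year test: 258.7 to 262.7 weeks after radiotherapy. From the latest baseline, 4.62 to 4.70 years. From the first injection, at least 265.7 to 269.7 weeks, or 5.09 to 5.17 years. Share: 24.4 / 265.7 to 24.4 / 269.7, about 9%.

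Change of Wechsler instrument by the 4-year test:
- The youngest eligible patient is 3 at baseline, so at least 3 + 4.62 = 7.6 at the 4-year test. That is past both stated switch ages, so everyone aged 3 to 6 at baseline changes instrument.
- A patient over 6 but under 7 at baseline changes under the instrument descriptions but not under Table 1.
- Upper switch: 16 − 4.70 = 11.3 to 16 − 4.62 = 11.4 for the latest baseline, and 16 − 5.17 = 10.8 to 16 − 5.09 = 10.9 for a test before the first injection. Patients from about 11 up to 16 therefore also change.

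Size in score units: if e is the mean change that precedes a late baseline and f the share of patients tested late, the pooled mean change omits f × e. The documents give neither. Assuming f from 0.25 to 1 and a loss e of 0.10 to 0.50 SD gives 0.025 to 0.50 SD. That range only reflects the assumptions, and even the sign of e is not known from the documents.

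**The case against.** Section 10 discloses the window and marks the word baseline as loosely used. The window is permissive: it allows an early test and forces no late one. Section 8 works as an eligibility checklist and also omits the audiogram and neuroendocrine work-up that Section 10 requires at baseline. Its silence is therefore weak evidence about when neuropsychological testing was planned, and Appendix B may say more. All of this stands. A reader might infer that the trial has no pre-treatment neuropsychological data, or that every baseline follows radiotherapy. The documents do not support either. They show only that a late baseline is allowed and that Section 14 does not handle it.

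It can also be said that the aim is long-term morbidity, that Section 11.2 classes neurocognitive dysfunction as a late effect, and that only about 9% of the span to the 4-year test precedes the latest baseline. This limits the point, because effects that emerge later remain visible. But calendar share is not exposure share: both injections and all 30 fractions fall inside that 9%. Equally, neither percentage measures bias.

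The z-scores at each visit compare patients with norms without any baseline, and Section 14 has no test or decision rule on these scores. That also stands, and it keeps this a matter of interpretation.

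Finally, splitting at most 20 patients gives small groups, and a pre-radiotherapy test is itself affected by recent surgery, since therapy starts within 42 days of resection. True, but a labelled split or listing is easier to interpret than an unlabelled mixture.

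**Conclusion.** The point holds as a matter of interpretation. Followed as written, Section 14 can pool pre- and post-radiotherapy references and can subtract raw scores from different instruments. The latest permitted baseline comes at least 24.4 weeks after the first injection, after 30 of 30 fractions, 14 of 32 vincristine doses and 2 of 8 cycle starts. These figures rest on the protocol's approximate intervals and on the reading of treatment completion given above.

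No size in score units can be given, because the share tested late and the early change are not in the documents. A reader might infer that the plan understates neurotoxicity, or that the third objective cannot be met. Neither follows: the direction of early change is unknown, and z-score levels against norms are unaffected. The instrument problem is certain for ages 3 to 6 at baseline; between 6 and 7 it depends on which part of Section 10 is followed. This is a change to consider, not a flaw in the trial's main analysis.

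**What to change.** In Section 14:

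1. Record each baseline test date relative to the first 131-I-3F8 injection and to the start and end of radiotherapy.
2. Show change from baseline separately for pre- and post-radiotherapy baselines, listing any test done during radiotherapy on its own. Use individual listings if the groups are very small. Label post-radiotherapy baselines as a post-radiotherapy reference, and state that change from them cannot show effects that arose before the test.
3. Base change over time on the age/sex-adjusted z-scores. Compute no raw-score change across different instruments; raw scores can still be tabulated by visit. State which switch age applies, since Table 1 and the instrument descriptions differ.
4. As a minor edit, align the annual visits named in Section 14 with the 1- and 4-year schedule in Section 10.

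The cost is a few sentences and one recorded date per patient; no testing time changes. The downside is very small descriptive groups, smaller still by year 4 because Section 13 removes patients at progression. Pre-radiotherapy tests may follow an injection, which the dates would show, and they follow recent surgery, so neither group isolates the regimen's effect.

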Medulloblastomas are highly malignant tumors that are very unlikely to be cured by surgery alone due to either recurrence at the primary site or dissemination through the cerebrospinal fluid (CSF) to distant leptomeningeal sites. The use of post-operative RT can be curative. The historical approach was to use RT without chemotherapy, with doses of 3600 cGy craniospinal, with a boost to 5400 cGy to the posterior fossa. Several recent studies have indicated that this approach produces an approximate 5-year event-free survival rate of 60% in patients with standard-risk disease. However, these doses of RT are associated with a significant risk of severe chronic neuropsychological and neuroendocrine morbidities, and growth retardation, as will be described below. These problems can be ascribed both to the craniospinal component of the radiation treatment and also to the temporal lobe and auditory apparatus inadvertently receiving a significant proportion of the boost dose when conventional treatment techniques are utilized. An attempt to reduce the craniospinal dose to 2340 cGy without the addition of chemotherapy in patients with standard-risk disease resulted an increased risk of early relapse, early isolated neuraxis relapse and a strong trend towards lower 5-year event-free survival ($p=0.080$).¹

However, in single-arm studies, the addition of chemotherapy appears to both improve event-free survival and to allow the use of reduced-dose craniospinal RT. The Children's Cancer Group treated 65 children between 3 and 10 years of age with non-metastatic medulloblastoma with reduced-dose craniospinal RT (2340 cGy) and a boost to the posterior fossa to 5580 cGy. Patients also received weekly vincristine during the RT and beginning 6 weeks after completion of RT began a planned eight cycles of vincristine, cisplatin and lomustine chemotherapy. Progression-free survival was 86% +/- 4% at 3 years and 79% +/- 7% at 5 years. Hearing loss (presumably due to both cisplatin and RT to the auditory apparatus) occurred in 32%. Neuropsychological outcome was not described.² This regimen has been explored on a larger scale in CCG-9961. The study completed accrual in December 2000, but results are not yet available.

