Neuroendocrine assessment performed at baseline will include standing and sitting height, Tanner staging of puberty, free thyroxine, TSH, and bone age x-ray. For patients > 12-years-old or who have \geq Tanner 2 puberty, LH/FSH, and testosterone or estradiol will be assessed. Follow-up examinations will be performed until 5 years post-diagnosis and will consist of standing and sitting height, Tanner staging, free thyroxine, and TSH every 6 months. Growth hormone stimulation testing will be performed if yearly growth velocity post-treatment is < 4cm per year or at 2 years post-completion of all therapy, whichever occurs first. Bone age x-ray, and LH/FSH, and testosterone or estradiol for patients > 12 years or who have \geq Tanner 2 puberty, will be performed annually.

Assessment of tumor status via brain MRI will be performed about 4 weeks after completing RT (pre-cycle 1 chemotherapy), then about every 3 months while on therapy (prior to cycles 3, 5, and 7). After completion of therapy, brain MRI scans will be performed about every 3 months for 1 year, then every 6 months for 2 years, then every 12 months for 1 year. Total spine MRI scans will be performed at about 1 year, 2 years, and 3 years post-completion of therapy. Subsequent scans will be performed at the clinician's discretion and are not mandated by this protocol, but brain MRI scans are recommended to be done about annually.

Mandated evaluations including lab work, audiograms, and MRI scans may be performed at other (non-MSKCC) centers if deemed clinically indicated by an investigator. Outside MRI scans should be submitted to PACS, and reports submitted to medical records, as soon as possible.

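### Does timing spine MRI from the end of therapy, with no stated origin for the three-year failure count, let spinal relapses escape the stopping rule?

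*Combined protocol and SAP*

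**What the plan says.** Section 14.0 has one stopping rule: "We will stop the trial if 6 or more patients fail before 3 years". It gives no start date for the three years. The sentence on the control data just before it does carry one: "Of those who failed, half failed within the first 2 years of diagnosis". Section 12.0 defines a failure as clear progression or a death attributed to treatment, and accepts head MRI, spine MRI or CSF cytology as evidence. It has no rule for dating a failure.

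Section 8.0 requires a spine MRI and lumbar CSF cytology before treatment. In Section 10.0, imaging during therapy is of the brain only. After therapy, "Total spine MRI scans will be performed at about 1 year, 2 years, and 3 years post-completion of therapy", with brain MRI every three months for a year and then every six months for two years. The same section uses another clock for neuroendocrine follow-up: "Follow-up examinations will be performed until 5 years post-diagnosis".

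The survival objective in Section 2.0 is "To maintain or exceed the current progression-free survival rate for patients with standard-risk medulloblastoma", with no year attached. The benchmark in Section 3.0 is: "Progression-free survival was 86% +/- 4% at 3 years and 79% +/- 7% at 5 years".

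**The concern.** The failure count and the spine scans appear to run on different clocks. If three years are counted from diagnosis, surgery or start of therapy, only one post-therapy spine scan is scheduled before the limit, and the next falls shortly after it. A relapse that is silent, confined to the spine and arises between that first scan and month 36 would be found too late to count. The error has one direction: fewer counted failures, less stopping and a better-looking three-year result. The spine matters here because Section 11.0 itself names extra failures from the lower craniospinal dose as a risk. With no origin written down, whether a relapse on the second spine scan counts could in principle be settled after it had been seen.

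**Working it through.** **1. The plan's own figures.** With 20 patients and a limit of 6, the exact binomial tail P(X ≥ 6) is 6.7% at a 15% failure rate, 38.3% at 25% and 75.5% at 35%. The plan states 7%, 23% and 76%. The first and third reproduce. The middle one does not, but that is a separate matter and nothing below uses it.

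**2. When therapy ends.** Weeks from start of therapy or from surgery (diagnosis taken as at surgery, an assumption):

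| Step | Weeks | Source |
|---|---|---|
| Surgery to start | 0–6 | 6.1 (0 if counted from start) |
| First to second injection | 1 | 9.1.2 |
| Second injection to radiation | 0–2 | assumption; 9.2 gives no interval |
| Radiation: 5400/180 = 30 fractions, 5 per week | 6 | 9.2 |
| Radiation to chemotherapy | 6 | 9.3 |
| Eight six-week cycles, to the last dose (7 × 6 + 2) or the end of cycle 8 | 44–48 | 9.3 |

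The total is 57 to 69 weeks, or 13.1 to 15.9 months.

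**3. Where the spine scans fall.** Adding 12, 24 and 36 months gives months 25.1–27.9, 37.1–39.9 and 49.1–51.9. The last scan before month 36 precedes it by 36 − 27.9 = 8.1 to 36 − 25.1 = 10.9 months. The next follows it by 1.1 to 3.9 months. The gap depends on the schedule: with one cycle fewer on the fastest path, therapy ends at 51 weeks (11.7 months) and the second scan falls at 35.7 months, inside the limit.

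**4. How much the choice of clock matters.** The benchmark loses 86 − 79 = 7 points over 24 months, or 0.29 points per month (even timing assumed). Surgery and start of therapy differ by at most 42 days, or 1.4 months: 1.4 × 0.29 = 0.4 points, or 0.08 of 20 patients.

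**5. Size of the gap effect at the benchmark.** By three years 14% fail, or 2.8 of 20. The share of those failing in year 3 is (14 − 7)/14 = 50% if the stated half refers to three-year failures. It is (14 − 10.5)/14 = 25% if it refers to the 21% failing by five years. With even timing within the year, the share arising after the first spine scan is 0.25 × 8.1/12 = 17% to 0.50 × 10.9/12 = 45%. That is 0.47 to 1.27 of 20 patients, of every relapse type. Only the silent spine-only part is lost:

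- if that is 10%: 0.05–0.13 patients, or 0.2–0.6 points of three-year PFS;
- if it is one third: 0.16–0.42 patients, or 0.8–2.1 points.

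This treats benchmark detection dates as onset dates, which is only a rough guide.

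**6. Effect on stopping.** If the true PFS in Section 14.0 means PFS as measured, the stopping probabilities do not change. If it means onset of relapse, take half of failures in year 3, a gap of 8 or 11 months and a silent share of 10–30%. The fraction moved past the limit is then 0.5 × 8/12 × 0.10 = 3.3% to 0.5 × 11/12 × 0.30 = 13.7%. The stopping probability falls from 6.7% to 3.6–5.9% at 85% PFS, and from 75.5% to 59.1–71.9% at 65% PFS.

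**7. Effect on enrolment.** The plan expects that its approach "will allow accrual to be approximately 6 patients per year". Entries two months apart put the twentieth patient at month 38, when only 2 of 20 have reached three years and 18–21% of the total time in the gap has elapsed. At the recent 3 to 4 per year the last entry is at month 76 or 57, with 11 or 8 patients at three years and 58–60% or 44–47% of gap time elapsed.

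**8. What the remedies would do.** Counting a relapse found on the spine scan nearest month 36 adds at most 0.29 × 1.1 to 0.29 × 3.9 = 0.3 to 1.1 points, or 0.06 to 0.23 of 20 patients, that arose after the limit. Moving that scan to month 36 lengthens the interval to the third from 12 to 13.1–15.9 months.

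**The case for a change.** The best case for a change is that it costs a sentence. The rule is the only stopping rule shown, its clock is unstated, and the candidate clocks are far apart if end of therapy is one of them: 13.1 to 15.9 months × 0.29 = 3.8 to 4.6 points, or 0.8 to 0.9 of 20 patients of any relapse type. If the regimen fails badly, the loss could also approach one patient: at 65% PFS with a 30% silent share and an 11-month gap it is 20 × 0.35 × 0.137 = 0.96.

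The missing origin is real, and stating it would do no harm. The rest is weaker:

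- End of therapy is not a serious candidate. The control data to which the rule is calibrated are counted from diagnosis, and Section 12.0 counts treatment deaths, many of which would precede such a clock. It would also place the third spine scan on the limit, so a boundary question would remain.
- The missing origin does not cause the gap. With diagnosis written in, the second spine scan still falls after month 36.
- The 0.96 figure is the extreme corner of an assumed range, and it matters only if PFS is read as onset rather than detection.
- Section 3.0 describes isolated neuraxis relapse after reduced-dose radiation without chemotherapy as early, which a scan at months 25–28 can catch. Its small 1800 cGy series reports distant recurrences, but does not call them spinal or silent.

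**Conclusion.** No change is needed. The plan leaves out a detail that analysts would fill the same way, to within weeks and about 0.08 of 20 patients. The misalignment between spine scans and month 36 is a trade-off in surveillance. Any periodic schedule dates a silent relapse at the next scan, and the benchmark's imaging schedule is not given, so no bias against it can be shown.

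The likely size is 0.05 to 0.42 of 20 patients at the benchmark rate. This rests on all eight cycles being given on time, even timing of failures within year 3 and an assumed silent spine-only share of 10% to one third. Relapses with symptoms, brain disease or positive CSF, and those already visible at the first post-therapy spine scan, are unaffected. At the planned accrual there is little effect on the decision to stop enrolling.

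The remedies are open to dispute. A special counting rule would treat a spine relapse found at months 37–40 as a three-year failure, but not a brain relapse found on the brain MRI due at the same visit. It would also depart from the definition behind the 86% benchmark. Moving the scan widens a later interval. The content of Appendix B, which tabulates the required observations, and the text between Sections 14.0 and 15.2 were not available and could bear on the timing.
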